### 3.6.1 Criteria for removal from protocol therapy

- Completion of study therapy
- Progressive disease
- DLT if clinically indicated.
- Intercurrent illness or medical circumstances.
- Voluntary withdrawal from the treatment regimen
- PI determines further treatment on this study is not in patient's best interest
- Patients who are off-treatment but still on-study will be followed as per the schedule in [Appendix A: Study Calendar](#), until they begin alternative therapy or voluntarily withdrawal from follow-up testing. Thereafter, they may be followed on-study for survival and other secondary endpoints.
- Positive pregnancy test

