### 10.4.3 Analysis of the secondary efficacy endpoints

Progression-free survival (PFS) will be determined using the Kaplan-Meier method, considering those who progress or die without progression as failures, and censoring those who do not.

Overall survival (OS) will be determined using the Kaplan-Meier method.

Each of these will be calculated starting from the date the patient enrolled onto the trial. Appropriate confidence intervals will be reported for each of these measures.

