## 16 APPENDICES

### 16.1 APPENDIX A: STUDY CALENDAR

	Screening 	All Cycles (28 days each)												EOT visit	Follow up 	
		C1 D1	C1 D15	C2 D1	C2 D15	C3 D1	C3 D15	C4 D1	C4 D15	C5 D1	C5 D15	C6 D1	C6 D15 & Beyond			
History/PE incl weight and skin assessment 	X	X	X	X	X	X	X	X	X	X	X	X	X	X	X	
Confirmation of pathology/Biopsy 	X					X									X	
ECOG, Vital Signs	X	X	X	X	X	X	X	X	X	X	X	X	X	X	X	
Tumor evaluation/measurements	X					X				X			X 			
M7824 		X	X	X	X	X	X	X	X	X	X	X	X	X		
Lab assessments 	X	X	X	X	X	X	X	X	X	X	X	X	X	X	X	X
Pregnancy test 	X	X		X		X		X		X		X				
Lymphocyte phenotyping 	X															
ECG	X															
CT C/A/P or CT C+MRI A/P 	X					X				X			X 	X		
Follow-up Phone calls/emails																X 
Correlative Studies	Please refer to Section 5.2															

*Abbreviated Title: Phase II M7824 in UC*  
*Version Date: 06/23/2021*

1. Pre-treatment tissue biopsy and/or tissue availability is mandatory. On-treatment biopsy is required unless obtaining biopsy is not technically or clinically feasible. Post-treatment biopsy is optional.
2. Tests done at screening do not need to be repeated on baseline (C1D1) if performed within 21 days prior to initiation of study therapy.
3. M7824 will be delivered intravenously every 2 weeks (+/- 3 days).
4. Vital signs must be measured within 30 minutes before and 30 minutes following M7824 infusions. In addition, at least one time during the infusion of M7824.
5. Laboratory assessments: CBC with differential, acute care panel (sodium, potassium, chloride, total CO2 (Bicarbonate), creatinine, glucose, urea nitrogen), mineral panel (albumin, calcium total, magnesium total, phosphorus), hepatic panel (alkaline phosphatase, ALT/GPT, AST/GOT, total bilirubin, direct bilirubin), ionized calcium, amylase, lipase, TSH with reflex T3 and T4, LDH, total protein, GGT, PT/INR, PTT, and urine analysis. Hepatitis B and C will be done at screening only.
6. For females of childbearing-potential (within 3 days prior to initiation of study therapy).
7. Lymphocyte phenotyping tests will be done to check the eligibility of HIV positive patients. HIV-positive patients are eligible only if CD4 counts are greater than 350 cells/mm^3 and viral load is undetectable.

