8. CT of chest, abdomen and pelvis with IV contrast (oral contrast as indicated) or CT of the chest without contrast and MRI abdomen/pelvis with tumor measurements. For this study patients should be re-evaluated for response every 8 weeks (+/- 10 days). If a scan identifies objective response or progressive disease, a confirmatory scan should be obtained 4-8 weeks following initial documentation of objective response or progression. In patients with clinical progression or unequivocal scan, confirmatory progression scan can be deferred. Scans will continue every 8 weeks until disease progression or start of a new anti-cancer treatment.
9. After disease progression or in those subjects who were removed from study therapy for reasons other than disease progression, subjects will be followed every 12 weeks in clinic or by telephone/email for assessment of survival status, related adverse events and documentation of initiation of new anti-cancer therapy.
10. If appropriate screening imaging is done within 21 days of C1D1 repeat screening imaging is not required.
11. All SAEs ongoing at the 30-day (+/- 10 days) safety follow-up visit must be monitored and followed up by the investigator until stabilization or until the outcome is known, unless the subject is documented as "lost to follow-up." In addition, all trial drug-related SAEs occurring after 30 day safety follow up visit and ongoing at the Safety Follow-up visit have to be followed up in the same manner.
12. Skin assessment must be performed at baseline and at least every 6 weeks during treatment and at the end of treatment or 28 (±5 days) days post-treatment safety follow-up (if not performed in the previous 6 weeks).

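### Footnotes 8 and 9 of the study calendar give inconsistent imaging instructions for patients who stop study drug without progression, so off-treatment scans may be missed

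*Combined protocol and SAP*

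**What the plan says.** Appendix A (Section 16.1), footnote 8: "Scans will continue every 8 weeks until disease progression or start of a new anti-cancer treatment". Stopping study drug is not listed as a reason to stop scanning. The same footnote and Section 6.3 both ask for a confirmatory scan 4 to 8 weeks after a first response, with no condition that the patient is still on drug.

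Footnote 9 covers two groups together: "After disease progression or in those subjects who were removed from study therapy for reasons other than disease progression". For both, "subjects will be followed every 12 weeks in clinic or by telephone/email for assessment of survival status", together with related adverse events and new therapy. No tumor assessment is listed.

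Both footnotes are attached to the calendar row "CT C/A/P or CT C+MRI A/P". No imaging mark is visible in that row under Follow up.

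Section 3.6.1 points back to the calendar: "Patients who are off-treatment but still on-study will be followed as per the schedule in" Appendix A, "until they begin alternative therapy or voluntarily withdrawal from follow-up testing". It then adds: "Thereafter, they may be followed on-study for survival and other secondary endpoints".

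Section 10.4.3 defines PFS by "considering those who progress or die without progression as failures, and censoring those who do not". It gives no censoring date and no rule for a patient who stops drug without progression.

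**The concern.** A patient who has progressed needs no further scans for PFS or ORR. A patient who stops for toxicity without progression does. Footnote 9 treats the two alike, and telephone or email contact cannot measure a tumor. Because footnote 9 hangs on the CT row, a site can reasonably take it as the imaging rule for anyone off drug.

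Two endpoints are exposed if that happens:

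- **PFS.** Progression after stopping is dated late or not at all. If only a later death is then counted, PFS is probably biased upward.
- **ORR (primary).** Section 6.3.3.3 makes best response depend on confirmation, and its table requires confirmation at 4 weeks or later for a trial of this type. A response first seen shortly before stopping could lack its second scan and count as a non-response.

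Such patients are foreseeable. Section 3.3.1 does not allow dose reductions, and Section 3.3.1.2 requires discontinuation for many Grade 3 and most Grade 4 drug reactions.

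**Working it through.** **1. The instructions side by side, for a patient who stops without PD**

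| Place | What happens after stopping | What ends it |
|---|---|---|
| Footnote 8 | Imaging every 8 weeks, plus confirmatory scan | PD or new therapy |
| Footnote 9 | 12-weekly contact; survival, related AEs, new therapy | Not stated |
| Calendar, Follow up | No imaging mark visible | – |
| Section 3.6.1 | Appendix A schedule | Alternative therapy, or withdrawal from testing |
| Section 6.3 | Imaging every 8 weeks, every 12 weeks after one year; confirmatory scan | Not tied to treatment |
| Section 10.4.3 | PD or death is an event, others censored | No censoring date |

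Section 3.6.1 leans towards footnote 8 but sends the reader back to the calendar holding both footnotes. Footnote 8 and Section 6.3 also differ on the interval after year 1.

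**2. The plan's own design figures (Section 10.2)**

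Early termination probability under p0 is P(X1 ≤ r1):

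- 1A: 0.85^9 + 9 × 0.15 × 0.85^8 = 0.2316 + 0.3679 = 0.5995 (stated 60.0%)
- 1B: 0.90^8 = 0.4305 (stated 43.1%)
- 2A and 2B: 0.95^12 = 0.5404 (stated 54.0%)

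The probability of declaring success at response rate p is the sum over x1 > r1 of b(x1; n1, p) × P(Bin(n − n1, p) ≥ r + 1 − x1). At p0 this gives actual alpha of 0.074/0.054/0.043/0.080, within the 0.10 limit. At p1 it gives power of 81.5/90.5/80.1/80.3%, meeting the 80/90/80/80% targets. The stated designs are sound.

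**3. If a share u of true responses goes unconfirmed**

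Replace p1 by p1 × (1 − u). At u = 5% the rates become 0.380, 0.380, 0.2375 and 0.190. The documents do not give u.

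| u (assumed) | 1A | 1B | 2A | 2B |
|---|---|---|---|---|
| 0 | 81.5% | 90.5% | 80.1% | 80.3% |
| 5% | 77.0% | 87.6% | 76.8% | 77.2% |
| 10% | 71.8% | 84.1% | 73.1% | 73.7% |
| 15.8% | 65.0% | 79.2% | 68.4% | 69.2% |

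The 15.8% is 3/19, the patients in the phase I study (Section 1.2.3) who stopped for treatment-related AEs at any time. It is only an upper bound at that stop rate: it would need every such stop to fall between first response and confirmation, and every confirmatory scan to be skipped.

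**4. How many patients stop**

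3/19 × 68 = 10.7, so roughly 10 of the 68 evaluable patients at the phase I rate.

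**5. PFS, illustration only**

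All inputs except 3/19 and the scan interval are assumptions: exponential times, median PFS 3 months, median 6 months from PD to death, 8-weekly scans. Six-month PFS:

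| Stop before PD; hazard after stopping | Everyone scanned | Censored at stop | Only death counted after stop |
|---|---|---|---|
| 15.8%; unchanged | 28.0% | 26.7% | 32.6% |
| 15.8%; doubled | 25.2% | 26.7% | 31.7% |
| 30%; doubled | 22.4% | 25.1% | 35.9% |

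Counting only deaths distorts PFS more than censoring does. With an unchanged hazard the censoring is not informative; the small gap there comes from scan timing.

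**The case against.** The strongest reply is that the plan already requires these scans. Footnote 8 does not end imaging when drug stops, and footnote 9 nowhere says that imaging stops. Attached to the same row, the two can be read as 8-weekly scans plus 12-weekly contacts. Section 3.6.1 in full assumes that testing continues off treatment until alternative therapy, with survival follow-up only thereafter. The note under the response table in Section 6.3.3.3 asks for progression to be documented after discontinuation in patients with symptomatic deterioration. The confirmatory scan is required whatever the treatment status. Dosing may also be delayed up to 12 weeks (Section 3.3.1), so a toxicity hold is not automatically a removal. PFS is secondary and carries no test.

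Most of this stands, and it rules out a stronger reading that a reader might infer: that PFS is informatively censored and that some responses cannot be confirmed. Informative censoring would need scans to stop, patients to be censored at that point, and their risk to change afterwards; under Section 10.4.3 a later death still counts as a failure. Lost confirmation would need a site to apply footnote 9 and overlook both statements of the confirmatory scan.

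The blank Follow-up cell is supporting evidence only. Column alignment in the extracted table is uncertain, since the M7824 marks appear to run into the end-of-treatment column. It should be checked against the original.

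The reply does not remove the inconsistency. Footnote 9 still gives patients without progression the same imaging-free follow-up as progressed patients, and no text says that it adds to footnote 8.

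**Conclusion.** The instructions are inconsistent and should be reconciled. The consequence is conditional: missed scans, late or missing progression dates and unconfirmed responses arise only where a site applies footnote 9 alone.

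The size is unknown. If 5% of true responses went unconfirmed, power would fall by 2.9 to 4.5 percentage points and every cohort would sit below its target. The 65 to 79% power figures at 15.8% mark an outer limit and should not be read as an expectation. For PFS the direction is probably upward if only deaths are captured after stopping; the amount depends on assumptions that the documents do not supply. No planned sample size or decision threshold needs to change. The case for acting now is that missed scans cannot be recovered at analysis.

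**What to change.** Reconcile footnotes 8 and 9, Section 3.6.1 and Section 6.3:

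- Split footnote 9 by progression status. State that patients off therapy without PD stay on the protocol's tumor-imaging schedule, including the response-confirmation scan, until PD, new anti-cancer therapy, withdrawal or death. The 12-weekly contact alone then applies after PD.
- Mark CT and tumor evaluation in the Follow-up column, with that condition.
- Give one consistent scan interval after year 1; footnote 8 has 8 weeks and Section 6.3 has 12.
- Alongside this, a sentence in Section 10.4 should state the PFS censoring date and how an unconfirmed response is counted.

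The cost is an edit to the calendar and text, plus a few scan visits for roughly 10 patients, which footnote 8 already calls for.

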**16.2 APPENDIX B: PERFORMANCE STATUS CRITERIA**

ECOG Performance Status Scale		Karnofsky Performance Scale	
Grade	Descriptions	Percent	Description
0	Normal activity. Fully active, able to carry on all pre-disease performance without restriction.	100	Normal, no complaints, no evidence of disease.
		90	Able to carry on normal activity; minor signs or symptoms of disease.
1	Symptoms, but ambulatory. Restricted in physically strenuous activity, but ambulatory and able to carry out work of a light or sedentary nature (e.g., light housework, office work).	80	Normal activity with effort; some signs or symptoms of disease.
		70	Cares for self, unable to carry on normal activity or to do active work.
2	In bed <50% of the time. Ambulatory and capable of all self-care, but unable to carry out any work activities. Up and about more than 50% of waking hours.	60	Requires occasional assistance, but is able to care for most of his/her needs.
		50	Requires considerable assistance and frequent medical care.
3	In bed >50% of the time. Capable of only limited self-care, confined to bed or chair more than 50% of waking hours.	40	Disabled, requires special care and assistance.
		30	Severely disabled, hospitalization indicated. Death not imminent.
4	100% bedridden. Completely disabled. Cannot carry on any self-care. Totally confined to bed or chair.	20	Very sick, hospitalization indicated. Death not imminent.
		10	Moribund, fatal processes progressing rapidly.
5	Dead.	0	Dead.

## Appendix C: Management of ir AEs

## 16.2.1 Table A1 Management of Skin irAEs in Patients Treated With ICPis

1.0 Skin Toxicities	
1.1 Rash/inflammatory dermatitis	

Definition: Erythema multiforme minor (a targetoid reaction in the skin and mucous membranes usually triggered by infections, such as herpes simplex viruses, but can be associated with an immune-related drug eruption and if progresses to erythema multiforme major, it and can be a harbinger of SCAR, such as SJS), lichenoid (resembling the flat-topped, polygonal, and sometimes scaly or hypertrophic lesions of lichen-planus), eczematous (inflammatory dermatitis characterized by pruritic, erythematous, scaly, or crusted papules or plaques on the skin, which is vulnerable to superinfection, psoriasiform [resembling the well-demarcated, erythematous, and scaly papules and plaques of psoriasis], morbilliform [a nonpustular, nonbullous measles-like exanthematous rash of the skin often referred to as “maculopapular” and without systemic symptoms or laboratory abnormalities, excluding occasional isolated peripheral eosinophilia, palmoplantar erythrodysesthesia [hand-foot syndrome; redness, numbness, burning, itching, and superficial desquamation of the palms and soles], neutrophilic dermatoses [eg, Sweet syndrome], and others)
	
Diagnostic workshop	

Pertinent history and physical examination
 
Rule out any other etiology of the skin problem, such as an infection, an effect of another drug, or a skin condition linked to another systemic disease or unrelated primary skin disorder
 
If needed, a biologic checkup, including a blood cell count and liver and kidney tests
 
Directed serologic studies if an autoimmune condition is suspected, such as lupus or dermatomyositis: a screening antinuclear antibody test, SS-A/Anti-Ro, SS-B/Anti-La if predominantly photodistributed/photosensitivity, antihistone, double-stranded DNA, and other relevant serologies. Consider expanding serologic studies or diagnostic work-up if other autoimmune conditions are considered based on signs, symptoms Skin biopsy
 
Consider clinical monitoring with use of serial clinical photography
 
Review full list of patient medications to rule out other drug-induced cause for photosensitivity
	
Grading	Management
Grading according to CTCAE is a challenge for skin. Instead, severity may be based on BSA, tolerability, morbidity, and duration.	
G1: Symptoms do not affect the quality of life or controlled with topical regimen and/or oral antipruritic	
Continue ICPi
 
Treat with topical emollients and/or mild-moderate potency topical corticosteroids
 
Counsel patients to avoid skin irritants and sun exposure

G2: Inflammatory reaction that affects quality of life and equires intervention based on diagnosis	
Consider holding ICPi and monitor weekly for improvement. If not resolved, interrupt treatment until skin AE has reverted to Grade 1
 
Consider initiating prednisone (or equivalent) at dosing 1 mg/kg, tapering over at least 4 weeks
 
In addition, treat with topical emollients, oral antihistamines, and medium- to high-potency topical corticosteroids

G3: As G2 but with failure to respond to indicated interventions for a G 2 dermatitis	
Hold ICPi therapy and consult with dermatology to determine appropriateness of resuming
 
Treat with topical emollients, oral antihistamines, and high-potency topical corticosteroids
 
Initiate (methyl)prednisolone (or equivalent) 1-2 mg/kg, tapering over at least 4 weeks

G4: All severe rashes unmanageable with prior interventions and intolerable	Immediately hold ICPi and consult dermatology to determine appropriateness of resuming ICPi therapy

1.0 Skin Toxicities	
	
upon resolution of skin toxicity and once corticosteroids are reduced to prednisone (or equivalent) <math>\leq</math> 10 mg
 
Systemic corticosteroids: IV (methyl)prednisolone (or equivalent) dosed at 1-2 mg/kg with slow tapering when the toxicity resolves
 
Monitor closely for progression to severe cutaneous adverse reaction
 
Should admit patient immediately with direct oncology involvement and with an urgent consult by dermatology
 
Consider alternative antineoplastic therapy over resuming ICPIs if the skin irAE does not resolve to G1 or less; if ICPIs are the patient's only option, consider restarting once these adverse effects have resolved to a G1 level

1.2 Bullous dermatoses	

Definition: Including bullous pemphigoid or other autoimmune bullous dermatoses, bullous drug reaction
 
Diagnostic work-up
 
Physical examination
 
Rule out any other etiology of the skin problem, such as an infection, an effect of another drug, or a skin condition linked to another systemic disease
 
If needed, a biologic checkup, including a blood cell count, liver, and kidney tests; consider serum antibody tests to rule out bullous pemphigoid or, under the guidance of dermatology, sending patient serum for indirect immunofluorescent testing to rule out other autoimmune blistering diseases
 
Referral to dermatology for blisters that are not explained by infectious or transient other causes (eg, herpes simplex, herpes zoster, bullous impetigo, bullous insect bite, friction or pressure blister)
 
Consider skin biopsy (both hematoxylin and eosin evaluation of lesional skin and direct immunofluorescence evaluation of perilesional skin)
	
Grading	Management

G1: Asymptomatic, blisters covering < 10% BSA and no associated erythema
	
If blisters are < 10% BSA, asymptomatic, and noninflammatory (such as the case with friction blisters or pressure blisters), cessation of ICPI is not necessary, and only observation and/or local wound care is warranted.
 
When symptomatic bullae or erosions, which are deroofed vesicles or bullae, are observed on the skin or mucosal surfaces, the cutaneous irAE is by definition considered at least G2
 
See G2 management recommendations

G2: Blistering that affects quality of life and requires intervention based on diagnosis not meeting criteria for Grade > 2
 
Blisters covering 10%-30% BSA
	
Hold ICPI therapy and consult with dermatology for work-up and to determine appropriateness of resuming
 
Attention given to general local wound care, which includes plain petrolatum ointment and bandages or plain petrolatum ointment gauze and bandage over any open erosions, which are left over on the skin after the blister has popped or if the roof of the blister easily sloughs off
 
Counsel patients to avoid skin irritants and overexposure to sun, wear protective clothing, use sunscreens
 
Work-up for autoimmune bullous disease as above
 
Initiate Class 1 high-potency topical corticosteroid (eg, clobetasol, betamethasone or equivalent) and reassess every 3 days for progression or improvement

1.0 Skin Toxicities	
	
Low threshold to initiate treatment with prednisone (or equivalent) at 0.5-1 mg/kg dosing and taper over at least 4 weeks
 
Monitor patients with G2 irAEs closely for progression to involvement of greater BSA and/or mucous membrane involvement. Consider following patients closely using serial photography
 
Primer on monitoring for complicated cutaneous adverse drug reactions:

	
Review of systems: Skin pain (like a sunburn), fevers, malaise, myalgias, arthralgias, abdominal pain, ocular discomfort or photophobia, sores or discomfort in the nares, sores or discomfort in the oropharynx, odynophagia, hoarseness, dysuria, sores or discomfort in the vaginal area for women or involving the meatus of the penis for men, sores in the perianal area, or pain with bowel movements

	
Physical examination: Include vital signs and a full skin examination specifically evaluating all skin surfaces and mucous membranes (eyes, nares, oropharynx, genitals, and perianal area). Assess for lymphadenopathy, facial or distal extremity swelling (may be signs of DIHS/DRESS). Assess for pustules or blisters or erosions in addition to areas of "dusky erythema," which may feel painful to palpation. To assess for a positive Nikolsky sign, place a gloved finger tangentially over erythematous skin and apply friction parallel to the skin surface. Nikolsky sign is positive if this results in detached or sloughing epidermis demonstrating poor attachment of the epidermis to the dermis, which is the case in some autoimmune disorders (eg, pemphigus) and SJS/TEN

G3: Skin sloughing covering > 30% BSA with associated pain and limiting self-care ADL	
Hold ICPI therapy and consult with dermatology to determine appropriateness of resuming
 
Administer IV (methyl)prednisolone (or equivalent) 1-2 mg/kg, tapering over at least 4 weeks
 
If bullous pemphigoid is diagnosed, it may be possible to avoid long-term use of systemic corticosteroids and treat with rituximab, as an alternative approach to treating the irAE
 
Seek infectious disease consultation if patient might have secondary cellulitis or if patient has other infection risk factors, such as neutropenia, etc.

G4: Blisters covering > 30% BSA with associated fluid or electrolyte abnormalities	
Permanently discontinue ICPI
 
Admit patient immediately and place under supervision of a dermatologist
 
Administer IV (methyl)prednisolone (or equivalent) 1-2 mg/kg with tapering over at least 4 weeks when the toxicity resolves
 
If bullous pemphigoid is diagnosed, it may be possible to avoid long-term use of systemic corticosteroids and treat with rituximab as an alternative approach to treating the irAE

1.0 Skin Toxicities	
	Seek infectious disease consultation if patient might have secondary cellulitis or if patient has other infection risk factors, such as neutropenia, etc
1.3 SCARs, including SJS, TEN, acute generalized exanthematous pustulosis, and DRESS/DIHS	
Definition: Severe changes in either structure or functions of skin, the appendages or the mucous membranes due to a drug Diagnostic work-up	
Total body skin examination with attention to examining all mucous membranes as well as complete review of systems Rule out any other etiology of the skin problem, such as an infection, an effect of another drug, or a skin condition linked to another systemic disease A biologic checkup, including a CBC with differential test, and liver and kidney function tests, including urinalysis, in addition to the blood work; if the patient is febrile, blood cultures should be considered as well Skin biopsies to assess for full-thickness epidermal necrosis, as is seen in SJS/TEN, as well as other possible etiologies like paraneoplastic pemphigus or other autoimmune blistering dermatoses or other drug reactions, such as acute generalized exanthematous pustulosis Consider following patients closely using serial clinical photography If mucous membrane involvement or blistering is observed on the skin, consider early admission to a burn center for further monitoring and management Primer on monitoring for complicated cutaneous adverse drug reactions: Review of systems: Skin pain (like a sunburn), fevers, malaise, myalgias, arthralgias, abdominal pain, ocular discomfort or photophobia, sores or discomfort in the nares, sores or discomfort in the oropharynx, odynophagia, hoarseness, dysuria, sores or discomfort in the vaginal area for women or involving the meatus of the penis for men, sores in the perianal area, or pain with bowel movements Physical examination: Include vital signs and a full skin examination specifically evaluating all skin surfaces and mucous membranes (eyes, nares, oropharynx, genitals, and perianal area). Assess for lymphadenopathy, facial or distal extremity swelling (may be signs of DIHS/DRESS). Assess for pustules or blisters or erosions in addition to areas of "dusky erythema," which may feel painful to palpation. To assess for a positive Nikolsky sign, place a gloved finger tangentially over erythematous skin and apply friction parallel to the skin surface. Nikolsky sign is positive if this results in detached or sloughing epidermis demonstrating poor attachment of the epidermis to the dermis, which is the case in some autoimmune disorders (eg, pemphigus) and SJS/TEN	
Grading	Management
All Grades	In cases of suspected SJS or any mucous membrane involvement, discontinue ICPI treatment and monitor closely for improvement, regardless of grade
G1: NA	For SCARs, there is no G1 category; if lower BSA is involved with bullae or erosions, there should remain a high concern that this reaction will progress to G3 or G4
G2: Morbilliform ("maculopapular") exanthem covering 10%-30% BSA with systemic symptoms, lymphadenopathy, or facial swelling	Hold ICPI and monitor patients closely every 3 days with G2 irAEs for progression to involvement of greater BSA and/or mucous membrane involvement Consider following patients closely using serial photography Initiate therapy with topical emollients, oral antihistamines, and medium- to high-strength topical corticosteroids Consider initiation of prednisone (or equivalent) 0.5-1 mg/kg tapered over at least 4 weeks
G3: Skin sloughing covering < 10% BSA with mucosal involvement associated signs (eg, erythema, purpura, epidermal detachment, mucous membrane detachment)	Hold ICPI therapy and consult with dermatology Treat skin with topical emollients and other petrolatum emollients, oral antihistamines, and high-strength topical corticosteroids; dimeticone may also be offered as an alternative to petrolatum

1.0 Skin Toxicities	
	
Administer IV (methyl)prednisolone (or equivalent) 0.5-1 mg/kg and convert to oral corticosteroids on response, wean over at least 4 weeks
 
Admit to burn and/or consult wound services with attention to supportive care, including fluid and electrolyte balance, minimizing insensible water losses, and preventing infection
 
Given the immune mechanism of action of these medicines, use of immune suppression is warranted and should be offered
 
For mucous membrane involvement of SJS or TEN, appropriate consulting services should be offered to guide management in preventing sequelae from scarring (eg, ophthalmology; ear, nose, and throat; urology; gynecology; etc, as appropriate)


G4: Skin erythema and blistering/sloughing covering <math>\geq</math> 10% to > 30% BSA with associated signs (eg, erythema, purpura, epidermal detachment, mucous membrane detachment) and/or systemic symptoms and concerning associated blood work abnormalities (eg, liver function test elevations in the setting of DRESS/DIHS)
	
Permanently discontinue ICPI
 
Admit patient immediately to a burn unit or ICU with consulted dermatology and wound care services
 
Consider further consultations based on management of mucosal surfaces (eg, ophthalmology; urology; gynecology; ear, nose, and throat surgery; etc) Initiate IV (methyl)prednisolone (or equivalent) 1-2 mg/kg, tapering when toxicity resolves to normal
 
IVIg or cyclosporine may also be considered in severe or corticosteroid-unresponsive cases
 
Consider pain/palliative consultation and/or admission in patients presenting with DRESS manifestations

Additional considerations: The usual prohibition of corticosteroids for SJS is not relevant here, as the underlying mechanism is a T-cell immunodirected toxicity
 
Adequate suppression is necessary with corticosteroids or other agents and may be prolonged in cases of DRESS/DIHS
 
All recommendations are expert consensus based, with benefits outweighing harms, and strength of recommendations are moderate
 
Abbreviations: ADL, activities of daily living; AE, adverse event; BSA, body surface area; CBC, complete blood count; CTCAE, Common Terminology Criteria for Adverse Events; DIHS, drug-induced hypersensitivity syndrome; DRESS, drug reaction with eosinophilia and systemic symptoms; G, Grade; ICPI, immune checkpoint inhibitor; ICU, intensive care unit; irAE, immune-related adverse event; IV, intravenous; IVIG, intravenous immunoglobulin; NA, not applicable; SCAR, severe cutaneous adverse reactions; SJS, Stevens-Johnson syndrome; TENS, toxic epidermal necrolysis.
	

